## **Intervention**

Participants who meet criteria for dysphagia on the videofluoroscopic swallowing examination will be randomly assigned into one of two groups: 1) a control group that will be receiving compensatory treatments only or 2) 12-week DF I-PRO therapy *plus* compensatory treatments, such as thickened liquids and/or postural strategies during natural swallowing activities for 12 weeks. Patients will be enrolled and trained in DF I-PRO therapy by [name] who regularly uses the SwallowSTRONG®-facilitated I-PRO therapy in clinical practice or a UW Voice and Swallowing clinician involved in this study who has been adequately trained in DF I-PRO therapy. Regardless of the treatment group to which a subject is randomized, they will be evaluated in the hospital at baseline and 8-week time points. If a patient in either group no longer meets criteria for dysphagia (Penetration-Aspiration Scale score of 3 or higher OR a rating of 2 on the Residue scale in any location) on the 8-week videofluoroscopic swallowing examination, s/he will no longer continue participation in the study. If a patient in either group remains dysphagic at the 8-week visit, s/he will continue participation in the study through the 12-week assessment point. [name] or a UW Voice and Swallowing clinician will conduct the 8 and 12 week assessments.

**Group 1: Compensatory treatments only:** This group will receive standard swallowing intervention, which is identified by the SLP as appropriate to treat the patient's dysphagia and is common clinical practice. This group is not receiving experimental therapy. Their therapy may include: 1) modifying the foods the subject eats or the fluids s/he drinks; 2) changing his/her posture when eating or drinking (for example, by a simple chin tuck) or using a swallowing maneuver while eating or drinking; 3) having him/her eat more slowly or in a quiet environment to make swallowing easier and safer; or 4) performing range of motion or vocal exercises for

swallowing or speech. Any progressive strengthening regimens or any type of lingual strengthening protocols specifically will be delayed until subjects have completed participation in this study in order to eliminate confounding influences on outcomes. No subjects will be at risk due to this delay as compensatory approaches mentioned above will be used and other strengthening regimens do not have enough evidence to support their inclusion in standard of care. Weekly check-in phone calls will be scheduled throughout the subjects' participation in the study.

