## **Specific Aims**

This randomized controlled pilot study will characterize effects of SwallowSTRONG® Device-Facilitated Isometric Progressive Resistance Oropharyngeal (DF I-PRO) therapy in a dose response framework on swallowing-related outcomes in a group of unilateral ischemic stroke patients. These results will be used to determine adequate sample size in order to support a larger clinical trial focused on the efficacy of this therapy approach for improving swallowing safety. This randomized study will expand upon previous work examining effects of this therapy approach on swallowing and health-related outcomes now limited to a heterogenous cohort of Veterans with dysphagia from a variety of etiologies. It will focus specifically on patients post-stroke who have been shown to experience improvements in swallow function following DF I-PRO therapy.

**Specific Aim 1:** To determine differences in swallowing physiology and bolus flow measures a) between a group of unilateral ischemic stroke subjects undergoing SwallowSTRONG® DF I-PRO therapy and controls and b) between 8 and 12 weeks of treatment.

**Hypothesis 1a:** Subjects treated with DF I-PRO therapy at both treatment duration points will demonstrate greater improvements in swallow physiology (isometric and swallowing pressures) as well as bolus flow measures (levels of airway invasion, post-swallow residue/stasis, oral transit times, and stage transition duration times) as compared to the control group.

**Hypothesis 1b:** Subjects treated with DF I-PRO therapy will experience improvements in swallow physiology and bolus flow measures at the 12 week duration compared to 8 weeks.

**Specific Aim 2:** To examine changes in level of oral intake and swallowing quality of life in post-stroke patients undergoing DF I-PRO therapy as compared to a control group and as they relate to treatment duration response at 8 weeks and 12 weeks

**Hypothesis 2a:** Patients undergoing DF I-PRO therapy will require less restrictive diets and will report improved swallowing-related quality of life compared to those in the control group at both treatment duration points.

**Hypothesis 2b:** Twelve weeks of DF I-PRO therapy will result in greater improvements (least restrictive diets and improved quality of life) compared to the 8 week duration.

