**Figure 1**

## **Visits**

**Baseline visit only:**

After the informed consent process has been completed but prior to videofluoroscopic examination of swallowing, each participant will complete a medical history questionnaire to ensure they meet inclusion/exclusion criteria. This questionnaire will include items related to current medical status, medical history, and medication usage. UW medical records also will be referenced to ensure the subject's eligibility for participation. As part of this screening, patients will undergo a urine pregnancy test to ensure they are not pregnant prior to participation. The Mini-Mental Status Examination (MMSE) will be administered only at baseline as a common examination of cognitive functioning. In addition, the Barthel index will be administered to assess severity of impairments in activities of daily living. For each patient, a form with demographics as well as a medication list will be filled out. These questionnaires and tests will take approximately 45 minutes to complete. For those subjects randomly assigned to Group 2, during this baseline visit, it also will take approximately 30 minutes to train the participant on how to do and record the exercises properly. In addition to the consent process and these procedures that will occur only at the baseline visit, the procedures described below will also be completed at this visit. The entire baseline visit will last about 2.5 hours. For the baseline visit and 8 week visit, videofluoroscopic examination of swallowing will need to be completed before the other procedures outline below as the outcome of that examination will determine the patient's continued participation in the study. If s/he does not meet criteria for dysphagia on the videofluoroscopic swallowing exam, s/he will either not be randomized to a study group (at baseline visit) or will not continue participation past the 8 week point (if dysphagia has resolved).

*Measures at each assessment point (baseline, 8 weeks, and 12 weeks):* The 8 week and 12 week visits will last about 90 minutes per session. The study includes up to 3 sessions which will require up to 7 hours in total. In addition if in Group 2, participation in the home exercises will last about 10 minutes per session, 9 sessions per week for up to 12 weeks, which will require up to 18 hours total.

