## **Statistical Analyses**

Prior to data analyses, the data collected under this study will be combined with data from its VA counterpart (IRB #2014-0939). Statistical analyses will be performed using this combined data set.

**Aim 1:** A repeated measures analysis model will be used to model changes in tongue strength in treatment and control groups, adjusted for age, gender, and baseline tongue strength. Each subject will have three observations: change between baseline and 8 weeks, baseline and 12

weeks, and 8 weeks and 12 weeks. This model will allow for comparison of differences between a) treatment durations (dose response) and b) between control and treatment groups.

**Aim 2:** Changes in oral intake and swallowing quality of life between baseline and 8 weeks, baseline and 12 weeks, and 8 weeks and 12 weeks will be modelled in a repeated measures analysis on treatment, adjusting for age, gender, and baseline outcome.

**Aim 3:** Change in number of new pneumonia diagnoses and number of hospital readmissions over a 1 year period, pre and post-study, will be modelled in linear regression models on treatment, adjusting for age, gender, and pre-study outcome.

All analyses will be performed on a randomized, or intention to treat basis, regardless of the actual treatment received. Study dropout by the subject will result in inclusion of incomplete data for that patient.

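### Observed week-12 data come only from subjects still dysphagic at week 8, yet the plan promises three change scores per subject and does not say whom its 12-week results describe

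*Combined protocol and SAP*

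**What the plan says.** **Exit rule.** Under Intervention, a subject in either group who is no longer dysphagic "on the 8-week videofluoroscopic swallowing examination, s/he will no longer continue participation in the study"; those still dysphagic go on to week 12. The Visits section (Baseline visit only) repeats that such a subject "will not continue participation past the 8 week point (if dysphagia has resolved" and adds: "The study includes up to 3 sessions".

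**Analysis.** Statistical Analyses, Aim 1, says: "Each subject will have three observations: change between baseline and 8 weeks". It then lists the changes from baseline to week 12 and from week 8 to week 12, and claims: "This model will allow for comparison of differences between a) treatment durations (dose response". Aim 2 uses the same three changes for oral intake and quality of life. No covariance structure is named.

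**Analysis set and missing data.** "All analyses will be performed on a randomized, or intention to treat basis, regardless of the actual treatment received". Then: "Study dropout by the subject will result in inclusion of incomplete data for that patient".

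**Hypotheses.** Hypothesis 1b says that treated subjects "will experience improvements in swallow physiology and bolus flow measures at the 12 week duration compared to 8 weeks". Hypotheses 1a and 2a compare the arms at both durations, and 2b compares 12 with 8 weeks on diet and quality of life. None is restricted to subjects still dysphagic at week 8.

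**Sizing.** The sample size section rests on the baseline-to-8-week pressure change, with 15 per group. Its allowance up to 40 enrolled is for subjects who fail the radiographic criteria at the initial examination.

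**The concern.** The three-observations sentence cannot be true of a subject who leaves at week 8. Being dysphagic at week 8 is an outcome measured after randomisation and possibly affected by treatment, so the subjects seen at week 12 need not be comparable between arms.

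Duration of therapy is a stated aim, and the pilot is meant to inform a larger trial. A 12-versus-8-week result obtained in persistently dysphagic subjects could be carried forward as if it applied to everyone randomised.

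Exits also make the answer depend on modelling choices the plan leaves open. With complete data and separate arm-by-interval means, the covariance structure does not alter the estimates. With exits it does.

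**Working it through.** **1. Which changes can exist**

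| Change | Exits at week 8 | Continues |
|---|---|---|
| Baseline to 8 weeks | yes | yes |
| Baseline to 12 weeks | no | yes |
| 8 to 12 weeks | no | yes |

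Three rows for each of 30 subjects is 90. The documents give no exit rate. If 20% exit in both arms (assumed), 24 continue: 24 x 3 + 6 x 1 = 78 rows. If 40% of therapy and 20% of control subjects exit (assumed), 9 + 12 = 21 continue: 21 x 3 + 9 x 1 = 72.

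**2. The plan's own figure**

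Two-sided two-sample t-test, 15 per group, difference 80 hPa, SD 100, alpha 0.05. The noncentrality is 80 / (100 x sqrt(2/15)) = 2.19 on 28 degrees of freedom, and power is 56.2%. The stated 56% is reproduced. It rests on 8-week change, which the exit rule does not touch.

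**3. Do the three rows agree after exits?**

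From the sample size section: mean 8-week gain 100 (therapy) and 20 (control), SD 100. Assumed: 8-to-12 change with mean 0 and SD 65, unrelated to recovery; swallowing recovery correlated r with the 8-week gain; exit of the best-recovered 40% (therapy) and 20% (control); compound symmetry, fitted by maximum likelihood with arm-by-interval means.

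In the therapy arm, those who continue have a mean 8-week gain below the arm mean by

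d = 100 x r x L, where L = phi(z_p)/(1 - p) = 0.644 at p = 40% (0.350 at 20%).

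Under compound symmetry with fitted correlation c, rows two and three are both regressed on row one with slope c. Hence:

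- row three = 0 + c x d
- row two minus row one = -d + c x d = -(1 - c) x d

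These should be the same quantity. They differ by exactly d.

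| r | d | fitted c | Row three | Row two minus row one |
|---|---|---|---|---|
| 0 | 0 | any | 0 | 0 |
| 0.3 | 19.3 | 0.51 | +10 | -9 |
| 0.5 | 32.2 | 0.53 | +17 | -15 |
| 0.7 | 45.1 | 0.56 | +25 | -20 |

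The cause is that the true slopes on row one are 1 for row two and 0 for row three, and a single c cannot represent both. With no exits, d = 0 and both readings are 0. Fits to large simulated data sets agree with these values. In 8,000 simulated trials of 15 per arm, row three averaged 0, 11, 18 and 25 hPa for the four values of r.

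A model on the two changes from baseline with unstructured covariance estimates the slope freely (here 1). It gives -d + 1 x d = 0, a single answer.

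**4. The 12-week arm difference (true value 80)**

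The three-row layout gives 80 - (1 - c) x 100 x r x (0.644 - 0.350).

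- r = 0.3: 80 - 0.49 x 8.8 = 76
- r = 0.7: 80 - 0.44 x 20.6 = 71

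The two-visit model gives 80. With equal exit in the two arms, both give 80. With the exit rates reversed, the three-row error is upward.

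**5. Limit of the two-visit model**

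If the later change is also related to recovery beyond the 8-week gain (assumed correlation 0.3, later-change SD 40 to 90), the two-visit therapy estimate for all randomised subjects is 4 to 9 hPa too low at 20% exit and 7 to 17 too low at 40%. It therefore rests on missing at random.

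**The case against.** **The exit is disclosed and has a rationale.** The visit text allows for fewer than three sessions, and the Dose Response background asks whether a subset needs longer treatment. Following only persistently dysphagic subjects fits that question. This stands, and the exit rule is not criticised here.

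**The dropout sentence may already cover it.** The sample size section uses the word dropout for subjects removed on radiographic criteria, so the missing-data sentence may be meant to include week-8 exits and to keep their week-8 values. This stands in part. The words limiting it to dropout by the subject leave it unclear, and keeping incomplete data does not say which population the 12-week estimate describes.

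**Intention to treat is promised.** The plan explains it as analysis by allocation. That is sound at week 8, but it does not supply week-12 values for subjects who left.

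**Two stronger readings are tempting.** A reader might infer that every 12-week result is unavoidably conditional on persistent dysphagia. It is not: a likelihood model using all week-8 data can target all randomised subjects under missing at random. What is conditional is the observed data. A reader might also infer that the three-row layout manufactures a benefit of longer therapy. The same fit yields an apparent gain or an apparent loss depending on which rows are read, and compound symmetry is an assumption because the plan names no structure.

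**Hypothesis 3a** is worded for subjects completing 12 weeks, while Aim 3 is analysed by allocation. Since the arm itself is named for 12 weeks of therapy, this may be loose naming and is a minor matter.

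**Conclusion.** The documentary conflict is certain: the exit rule and the promise of three observations per subject cannot both hold, and the plan does not state which population its 12-week results describe. This affects the 12-week parts of Hypotheses 1a and 2a and all of 1b and 2b.

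The layout problem is real but conditional. Under the assumed inputs, one fit contradicts itself by 19 to 45 hPa on the therapy-arm 8-to-12 change; with no exits, or with recovery unrelated to the 8-week gain, it does not. Exit rates, correlations, the later-change SD and the covariance structure are all assumptions. Neither the sign nor the size of any bias can be derived from the documents, and it may be zero.

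It should be fixed before analysis, mainly by wording. It does not undermine the trial.

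**What to change.** 1. Replace the three-observations sentence: one change for subjects who exit at week 8, and two changes from baseline for those who continue. State that the week-8 exit is handled as incomplete data, with week-8 values kept.
2. Fit a likelihood-based repeated measures model to the changes from baseline at weeks 8 and 12, with unstructured covariance. Take 8 to 12 weeks as a contrast from that model, not as a third row.
3. Name the two 12-week targets separately:
   - For subjects still dysphagic at week 8: the observed 8-to-12 change in those who continue, labelled as conditional, with any between-arm comparison labelled as not fully randomised.
   - For all randomised subjects: the model-based estimate, labelled as an extrapolation resting on missing at random, with a simple sensitivity analysis that shifts the unobserved week-12 values of exited subjects.
4. Treat the 8-week comparison as the one that includes all randomised subjects with week-8 data, in line with the sizing.

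Aligning the wording of Hypothesis 3a with the by-allocation analysis of Aim 3 is optional. The investigators must reconcile the Intervention, Visits and Statistical Analyses sections; no change to the clinical exit rule is proposed.

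**Cost.** Items 1 and 4 are wording. Items 2 and 3 use data already planned and need a little more analysis work. No visit or subject is added. The downside is narrower 12-week claims.

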**Group 2: SwallowSTRONG® device-facilitated I-PRO therapy plus compensatory treatments:**

[figure not shown]
Isometric tongue strengthening will be completed using the SwallowSTRONG® device (see Figure 1).

This device hand-held instrument provides numeric readout of pressure (hPa) and digital feedback of performance. It consists of a short cord (approx. 10 inches), which is attached to a small digital touch screen display. The 4-sensor array is custom-molded to the hard palate to ensure consistent placement.

Tongue press exercises consist of pressing the tongue against the sensors. Isometric exercises will focus on the anterior and posterior sensor. Subjects will be given a target pressure value for both the anterior and posterior sensor locations for which to aim during strengthening. Visual feedback on the display will signal the subject that they have attained their target pressure goal.

Prior to initiation of the strengthening regimen, baseline one repetition maximum (1RM) lingual pressures will be obtained at the anterior and posterior sensors independently by gathering 3 tongue press trials at each site that differ by less than 5% to adjust for variability in these measures. Subjects will take the SwallowStrong® device home with them and will complete 20 repetitions of the exercise (10 repetitions at the front sensor; 10 repetitions at the back sensor), three times per day on three days per week for twelve weeks. It will take approximately 10 minutes to complete 20 repetitions of the exercise resulting in about 30 minutes total for each home exercise session. During week one of the regimen, the target value of each repetition will be 60% of the 1RM. For the remaining eleven weeks of the program, the target value will be increased to 80% of the 1RM. These values of 60% and 80% were chosen based on previous work that employed progressive resistance training for the limbs and lingual musculature with healthy elders and patients post-stroke. At weeks three, five, seven, nine, and eleven, the baseline will be re-measured by phone and the 80% target value re-calculated. In addition, check-in phone calls also will be scheduled the other weeks of the study period.

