## **Outcomes**

The *primary outcome measure* will be changes in the *one repetition maximum (IRM) isometric lingual pressures* measured at the front and back sensors of the device. Secondary outcomes include *bolus flow durational measurements* taken from videofluoroscopic recordings, *swallowing pressures, SWAL-QOL scores, and FOIS scores*. In addition, we will compare the *number of pneumonia diagnoses* for community, hospital-acquired, and aspiration pneumonia for the same period of time prior to enrollment and following completion of the study (up to nine months). We also will track the *number of hospital re-admissions* for the same period of time prior to enrollment and following completion (up to 9 months). Treatment compliance also will be tracked within the SwallowStrong® device and will serve as a covariate in statistical analyses.

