*Saliva Analyses:* Each measure of viscoelasticity and lubrication properties will be recorded three times per sample. Apparent viscosity will be determined using a TA Discovery, HR-2 rheometer (TA Instruments, New Castle, DE, USA) equipped with a Peltier plate temperature control unit (233212.902). All measurements will be carried out with a flat plate geometry with a diameter of 20 mm and an operating gap of 200 µm. Each sample will first be allowed to equilibrate for 30 seconds at 37°C on the rheometer stage. Viscosity will then be measured at 37°C at shear rates ranging from 0.1 to 100 1/s. In [name] laboratory, samples will be frozen until all have been collected. Then, an enzyme-linked immunosorbent assay (ELISA) will be completed in order to quantify levels of the protein Substance P within the samples.

**Hospital Readmissions and Pneumonia Diagnoses:** The number of pneumonia diagnoses and overall hospital readmissions will be compared for the same period of time prior to enrollment and following completion of the study (up to 9 months) for each subject. Discharge reports will be used to tally the number of readmissions and clinic notes will be reviewed to determine number of pneumonia diagnoses (community, hospital-acquired, and aspiration pneumonia) for each subject.

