protocols will be recorded only by this code number. The link connecting the subject and code number will be password-protected stored separately in electronic format on the password-protected hospital network and only the PI ([name]) will have access. Only the approved project research staff ([name], [name]) will have access to the coded study data. All information about the subject will be treated confidentially and will not be revealed unless required by law. All HIPAA regulations pertaining to protection of participants and eliminating identification will be followed. Data will be de-identified at the close of the study. Any breach of confidentiality will immediately be reported to the IRB. Individual medical records will be accessed twice during the one year duration of this study: once by [name] initially to confirm the subjects' eligibility for the study and then again at the end of the study (one year point) to determine number of pneumonia diagnoses and hospital readmissions for the same number of months pre- and post-enrollment. Results of study-related procedures performed solely for research purposes (not standard of care) will not be placed in the subjects' medical record.

*Videofluoroscopic Swallowing Assessment:* Subjects are at risk for aspirating during the VFS assessment. If aspiration occurs during the VFS assessment, the particular bolus condition will be terminated once the cause of the aspiration is determined. Following completion of the study protocol, compensatory approaches to treatment (e.g., postures, diet modification) may be attempted in order to determine which strategies are most effective in reducing or eliminating the occurrence of airway penetration and/or aspiration, thereby ensuring safety with swallowing for patients in both treatment groups.

Subjects will be exposed to radiation exposure equivalent to one to two years of background radiation (less than 2.5 minutes) during the videofluoroscopic swallowing study. The risks of that amount are considered to be very small, and there is no indication of harmful effects to an individual. Subjects will not be included if they are pregnant. Radiation exposure during the VFS assessment will be limited as much as possible through attention to time restraints and adherence to ASHA's Guidelines for Speech-Language Pathologists Performing Videofluoroscopic Studies. Protective apparel with lead-shielding (lead apron, thyroid shield) will be worn at all times.

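### Aim 3 counts pneumonia and readmissions largely or wholly after the control arm's delay of strengthening has ended, and later strengthening is not recorded

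*Combined protocol and SAP*

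**What the plan says.** **Control condition.** Under Intervention, Group 1, progressive and lingual strengthening "will be delayed until subjects have completed participation in this study in order to eliminate confounding influences on outcomes".

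**End of participation.** Under Intervention, a subject in either arm who no longer meets the dysphagia criteria at the 8-week examination is released: "s/he will no longer continue participation in the study". A subject who is still dysphagic stays: "s/he will continue participation in the study through the 12-week assessment point".

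**Assigned regimen.** Group 2 exercises "three times per day on three days per week for twelve weeks", so the assigned therapy also ends no later than week 12.

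**Aim 3 window counted from completion.** Outcomes compares pneumonia diagnoses "for the same period of time prior to enrollment and following completion of the study (up to nine months") and readmissions "for the same period of time prior to enrollment and following completion (up to 9 months"). Data Reduction and Analysis repeats this: "prior to enrollment and following completion of the study (up to 9 months) for each subject". Statistical Analyses, Aim 3, also places the window before and after the study, but gives its length as one year.

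**Aim 3 window counted from enrolment.** Hypothesis 3a speaks of a change from before to after enrolment. Data Safety and Monitoring says "Individual medical records will be accessed twice during the one year duration of this study", the second time to count pneumonia diagnoses and readmissions over equal numbers of months before and after enrolment.

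**Analysis.** The Aim 3 model is a linear regression on treatment with age, gender and pre-study outcome, by intention to treat. No section plans to record or report strengthening that begins after a subject leaves the study.

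**The concern.** The protocol itself treats strengthening in controls as a source of confounding and delays it for that reason. The delay stops when participation stops. In three of the five places that define the Aim 3 window, that is also when counting begins. Two consequences follow under that wording. Events during the only period in which the arms are deliberately kept different are left out. Events are then counted while controls are free to start the kind of therapy that had been delayed.

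What is at stake is the meaning of Hypothesis 3a. It is framed as DF I-PRO against controls, but the count would compare immediate DF I-PRO with delayed or optional strengthening. Any uptake of effective strengthening among controls would shrink the difference, and without a record of uptake the report could not say by how much.

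**Working it through.** The plan gives no power or sample size for Aim 3. Its only power figures (Table 2) concern lingual pressure. They reproduce with a two-sided two-sample t-test, 15 per group, SD 100 hPa, alpha 0.05: 75.3%, 56.2%, 35.5% and 18.5% against the stated 75%, 56%, 35% and 18%. They do not bear on this point, which is a matter of timing.

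**1. Length of the delay in months**
- One month = 365.25 / 12 = 30.44 days.
- 8 weeks = 56 / 30.44 = 1.84 months.
- 12 weeks = 84 / 30.44 = 2.76 months.

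**2. Share of the Aim 3 window with the delay in force**

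Counting from completion (Outcomes, Data Reduction, Statistical Analyses): the window opens when the delay ends, so the share is 0% whatever its length.

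Counting from enrolment (Hypothesis 3a, Data Safety and Monitoring): share = length of delay / length of window.

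| Delay | 9-month window | 12-month window |
|---|---|---|
| 8 weeks | 1.84 / 9 = 20% | 1.84 / 12 = 15% |
| 12 weeks | 2.76 / 9 = 31% | 2.76 / 12 = 23% |

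On this reading 100% − 31% = 69% to 100% − 15% = 85% of the window falls after the delay ends. A much shorter window would behave differently: in a 3-month post-enrolment window, a 12-week delay covers 2.76 / 3 = 92%.

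The 9-month cap fits counting from completion: 12 − 2.76 = 9.24 months. That is suggestive only and does not settle which start date is meant.

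**3. Possible dilution**

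Let c be the fraction of controls who start strengthening at exit. The documents do not give c; 25%, 50% and 75% are assumed for illustration. Events are counted from completion, and events are taken to accrue evenly over the window.

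- Worst case, with benefit immediate and equal to Group 2's: retained = 1 − c.
- Delayed benefit, with none until a 12-week course is finished and equal benefit afterwards, in a 9-month window: retained = 1 − c × (1 − 2.76 / 9) = 1 − 0.693c.

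| c | Worst case | Delayed benefit |
|---|---|---|
| 25% | 75% | 83% |
| 50% | 50% | 65% |
| 75% | 25% | 48% |

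A less effective regimen or a later start would dilute the difference less than either column shows.

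**The case against.** **The start date is contradictory, not settled.** Hypothesis 3a and the record-review text would bring the 8 to 12 protected weeks into the count. This stands: it cannot be said flatly that those weeks contribute no events. It weakens the concern without removing it, because most of a 9 to 12 month window still lies beyond the delay.

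**Crossover is not documented.** No section offers controls the device or any strengthening after exit. The Group 1 text says that other strengthening regimens lack the evidence to be standard of care, and subjects released at week 8 are those whose dysphagia has resolved. This also stands. Against it, the same text describes a delay and not an exclusion, Data Safety and Monitoring allows that strengthening might form part of standard care, and the Intervention section says the trainer uses this therapy in routine practice. Uptake is possible and unknown.

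**A post-completion count is a legitimate question.** Group 2's assigned therapy has ended too, so such a count asks whether benefit lasts, and intention to treat keeps it valid for assignment. This is correct. A reader might infer that a null result could not be interpreted at all, but the documents do not support that: a carry-over benefit could still show, and the comparison of assignment stands. A reader might also infer that the pilot's event rates would mislead the sizing of the larger trial. The plan says its results will inform that sample size, but nowhere that event rates will be the basis, and it describes the larger trial as focused on swallowing safety.

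**A 12-week count is no better as the main comparison.** It measures events while therapy is still being delivered, whereas Hypothesis 3a concerns subjects who complete 12 weeks, and it would leave few events among about 30 subjects. This stands and limits the remedy.

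**Conclusion.** The point holds as one of timing and of missing information. Under the completion-based wording, the delay of strengthening covers 0% of the Aim 3 window and events during the 8 to 12 weeks of protected contrast are dropped. Under the enrolment-based wording, it covers 15% to 31% of a 9 to 12 month window. On neither reading is post-exit strengthening recorded.

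The likely direction is toward no difference. The size is unknown: the retained fractions in the working rest on assumed uptake of 25% to 75% and on equal benefit in those who start, and the 1 − c column is an upper bound on dilution, not a forecast. The documents do not show that controls will cross over. The randomised comparison is not invalidated; what it estimates is immediate DF I-PRO against delayed or optional strengthening. Aim 3 is not the primary outcome, so this affects what the pilot can say about health status and not its main result.

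**What to change.** 1. Reconcile Hypothesis 3a, Outcomes, Data Reduction and Analysis, Data Safety and Monitoring, and Statistical Analyses (Aim 3) on one start date and one window length. Count Aim 3 events from randomisation for every randomised subject, including those released at week 8, against an equal period before enrolment.
2. Report randomisation to week 12 separately, alongside the full window, against an equal pre-enrolment period. It need not become the main comparison.
3. In the end-of-study record review already planned, also extract whether and when each subject started any swallow-strengthening therapy after leaving the study, and report this by arm.
4. Describe the longer-window contrast in the light of that uptake, as immediate DF I-PRO against delayed or optional strengthening where controls have taken it up.

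The cost is wording changes and one added extraction field. The 12-week period will hold few events and its result will be imprecise. Nothing here alters treatment in either arm or the length of the delay.
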